2.2.3.1 Adverse Events

AEs (including SAEs and potential AESIs) will be recorded on the AE eCRF by the PI or designee if they occurred from the time of the first vaccination on Day 1 up to Month 13, regardless of causal association with the investigational product (IP). AE reporting is required for any new observation presenting after the first vaccination or for a deterioration of baseline condition (i.e., increased severity/frequency). From the signing of the ICF until immediately before the first vaccination on Day 1, only AEs resulting from a study-related procedure will be recorded on the AE eCRF; all other events reported in this time period will be recorded as signs and symptoms on the Medical History eCRF.

Refer to the specific sections in the Protocol EBS.AVA.212 on clinical laboratory tests ([Section 8.3.2](#)), PEs ([Section 8.3.3](#)), vital signs ([Section 8.3.4](#)), and e-diary reactogenicity ([Section 8.3.5.1](#)) for details on AE reporting based on participant observation and clinical test results.

2.2.3.2 Clinical Laboratory Assessments

All analytes to be tested during screening/safety clinical laboratory tests are specified in [Protocol EBS.AVA.212, Table 7](#).

The following assessments will be performed at Screening only:

- Urine drug screen (refer to Protocol EBS.AVA.212, Table 7 for analytes)
- Serologic testing (HIV-1/HIV-2 antibodies, HBV surface antigen, and HCV antibody). Confirmatory testing will be performed on any samples that test positive for either HIV or HCV; no additional blood/serum will be required for this confirmatory testing.
- FSH test to confirm postmenopausal status in women having > 12 consecutive months without menses (refer to [Protocol EBS.AVA.212, Section 5.1](#)).

Pregnancy testing will be performed at all visits including EWV. Female participants who are confirmed at Screening to be surgically sterile (refer to Protocol EBS.AVA.212, Section 5.1) are exempt from pregnancy testing. Vaccine will not be administered to any subject who tests positive for pregnancy.

Blood and urine samples for safety clinical laboratory testing (hematology, serum chemistry, urinalysis) will be collected at Screening and Day 29 as well as at the EWV if the EWV occurs before Day 29. Refer to Protocol EBS.AVA.212, Table 7 for the complete list of analytes to be tested. Blood samples for auto-antibody assessment of RF, ANA and anti-dsDNA antibodies and TSH will be taken at Day 1 prior to vaccination, Day 64/EWV, and at the time of unscheduled visit(s) if warranted from participant report(s) of potential AESI(s) at the safety follow-up phone call(s).

All samples will be sent to the central laboratory for analysis, except urine for pregnancy testing in women of childbearing potential (WOCBP), which will be performed at the site and results documented in the eCRF.

2.2.3.3 Physical Examination

A complete PE will be performed at Screening and Day 64/EWV. Symptom-directed PEs, a targeted examination of specific body systems based on the participant's complaint(s), will be conducted prior to vaccination on Days 1, 15, 29, and also during unscheduled visits occurring before Day 64.

2.2.3.4 Vital Signs

Vital signs including systolic and diastolic blood pressure (sitting), heart rate, respiration rate, and temperature will be obtained at Screening and each subsequent clinic visit through Day 64/EWV, including unscheduled visits occurring before Day 64. Height and weight will only be recorded at Screening. On vaccination days (Days 1, 5 and 29), vital signs will be assessed prior to vaccination and at 30 ± 5 minutes post vaccination.

2.2.3.5 E-Diary Reactogenicity

Reactogenicity (solicited systemic and injection site reactions) will be monitored by study site personnel for 30 minutes after vaccination and thereafter assessed daily by the

participants using e-diaries, starting on the evening after each vaccination, for at least seven days. If injection site or systemic reactions continue beyond seven days, participants will be prompted to continue diary entries until they are symptom-free for two consecutive days.

In the e-diary, information will be solicited on the following injection site reactions: warmth, tenderness, itching, pain, arm motion limitation, redness, induration, swelling, and bruising. In addition, information will be solicited on the following systemic reactions: tiredness, muscle ache, headache, and fever (oral temperature). The participant will be prompted to grade the severity of each reaction according to the instructions provided [e.g., Grade 0 (Absent)= symptom not present; Grade 1 (Mild) = symptom present but does not interfere with activities of daily living; Grade 2 (Moderate) = symptom causes some interference with activities of daily living; Grade 3 (Severe) = symptom prevents activities of daily living or requires treatment)].

Oral temperature (°F) will be recorded daily (at least once a day) by the participant in the e-diary.

Participants will also be asked to respond (yes/no) if they have taken pain/fever medications such as acetaminophen, aspirin, and nonsteroidal anti-inflammatory drugs (NSAIDs; e.g., ibuprofen) or other medication in the past 24 hours. Use of such medications recorded in the e-diary must be confirmed with the participant and recorded in the eCRF.

In addition to any reaction considered an AE by the PI, solicited reactions reported in the e-diary will be recorded by the PI or designee on the AE eCRF if they are serious [i.e., a solicited reaction will be considered ‘serious’ if confirmed by the investigator to be a Grade 4, or a Grade 3 that upon the investigator’s assessment meets any of the SAE criteria outlined in [Protocol EBS.AVA.212, Section 9.1.2](#)]; result in discontinuation of study product or withdrawal from the study; or remain unresolved for 14 days or more.

2.2.3.6 Data Safety Monitoring Board

Independent safety oversight will be provided by a DSMB, which will be notified of significant AEs (eg, SAEs, severe AEs recorded on eCRF, potential AESIs of autoimmune etiology, or any other events the MM deems medically relevant) as determined by the Medical Monitor on an ongoing basis. The DSMB will comprise at least three voting members, to include one expert in immunology to specifically support the evaluation of potential AESIs for autoimmune etiology, if pre-existing or new onset, and relationship to the study product. All DSMB reviews will be performed with blinded data, unless otherwise requested by the DSMB Chair. The operations of the DSMB will be detailed in a DSMB Charter.

2.3 Study Endpoints

2.3.1 Primary Endpoints

The primary study endpoints are as follows:

Lot Consistency:

- Equivalent immunogenicity across three consecutive AV7909 lots as demonstrated by the 95% confidence interval (CI) for the ratios of geometric mean TNA NF₅₀ at Day 64 for each of the three lot-to-lot comparisons to be within 0.5 and 2.0.
- Protective level of immunogenicity in all three consecutive AV7909 lots as demonstrated by the lower bound (LB) of the two-sided 95% CI to be $\geq 40\%$ for the proportions of AV7909 subjects in each of the three lots achieving a TNA NF₅₀ ≥ 0.56 at Day 64.

Both of the two lot consistency endpoints should be met to demonstrate AV7909 lot consistency.

Immunogenicity:

- Lower bound of the two-sided 95% CI is $\geq 40\%$ for the proportion of AV7909 participants in Groups 1-3 (three lots pooled) achieving a TNA NF₅₀ ≥ 0.56 on Day 64.
- Non-inferiority of AV7909 to BioThrax at Day 64 as determined by the two-sided lower 95% CI of the difference in the proportion of AV7909 participants (three lots pooled) with a TNA NF₅₀ ≥ 0.29 and the proportion of BioThrax participants with a TNA NF₅₀ ≥ 0.29 being greater than -15%.

Safety:

- Incidences of SAEs from the time of the first vaccination on Day 1 through the 12-month safety follow-up telephone call following the last vaccination.

2.3.2 Secondary Endpoints

The secondary study endpoints are as follows:

Immunogenicity:

- Lower bound of the two-sided 95% CI will be $\geq 67\%$ for the proportion of AV7909 participants in Groups 1-3 (three lots pooled) achieving a TNA NF₅₀ ≥ 0.15 on Day 29.

Safety:

- Incidences of AEs from the time of the first vaccination on Day 1 through Day 64.
- Incidences of clinical laboratory abnormalities.

- Incidences of autoimmune-associated AESIs from the time of the first vaccination on Day 1 through the 12-month safety follow-up telephone call following the last vaccination.
- Incidences of solicited systemic reactions and solicited injection site reactions by severity following each vaccination as reported in participant e-diaries.

2.4 Sample Size and Power Considerations

Sample size for this study is based primarily on safety considerations. The total sample size across all three AV7909 study groups is set at 3300 participants. Allowing a 10% drop-out rate, this sample size for safety (3000) is sufficient to detect, with 95% probability, an AE rate of 1:1000, or 0.1%.

It is expected that more participants will be excluded from the immunogenicity analysis population (Per Protocol [PP] Population; refer to [Section 3.2](#)) than excluded from the Safety Population. A 25% exclusion rate from the PP Population is assumed. Thus, the PP Population will include approximately 800 participants for each AV7909 group (2400 participants total) and 400 participants for the BioThrax group.

Even under the best manufacturing practices, between-lot variation exists and will be considered normal. It is assumed that the lot-to-lot geometric mean titer (GMT) ratio could be as low as 0.6 based on Emergent's experience with the BioThrax vaccine. Conservatively, the largest GMT ratio between two out of three lots is assumed to be 1.5. Assuming a coefficient of variation of 100% (slightly larger than the observed 91% in the phase 2 study, EBS.AVA.208), this study has >99% power to demonstrate lot consistency with the pre-specified equivalence bounds ([0.5, 2.0]) in terms of GMT ratio for TNA NF₅₀ at Day 64.

Based on the combined phase 1 and phase 2 data, the proportion of participants receiving two doses of AV7909 on Day 1 and Day 15 with TNA NF₅₀ at Day 64 over 0.56 is approximately 63% with lower 95% CI of 50% (total n = 54). Even assuming a conservative 50%, the study provides >99% power of rejecting the null hypothesis of 40% in each of the three AV7909 lots and in the combined AV7909 group (three lots pooled).

For the non-inferiority endpoint, among participants (n = 184) receiving BioThrax PEP regimen (3 doses, SC) in the EBS.AVA.006 study, 93.5% had TNA NF₅₀ values above 0.29 at Day 64. In the AV7909 phase 2 study (EBS.AVA.208), 86.5% of participants (n = 37) had TNA NF₅₀ above 0.29 at Day 64. Assuming a rate of 93% for the BioThrax group and 83% for the AV7909 group, the sample sizes of 400 and 2400 provide approximately 98% power to demonstrate non-inferiority of the two-dose AV7909 IM regimen to the three-dose BioThrax SC regimen at Day 64 with a non-inferiority margin of 15%.

The sample size calculation was performed using PROC POWER in SAS/STAT 9.4.

2.5 Randomization and Blinding

2.5.1 Randomization

At the Day 1 (randomization) visit, after the PI has confirmed that the participant meets all of the inclusion criteria and none of the exclusion criteria, the participant will be randomly assigned to one of the four study groups with the ratio of 2:2:2:1 (block size of 7) via an interactive voice and/or web response system (IxRS). Randomization will be stratified by site. Racial distribution will be monitored among recruited participants. Participants who are randomized and do not receive vaccination on the same day will be withdrawn from the study. Randomized participants who withdraw from the study for any reason will not be replaced in this trial.

A randomization plan describing the method of treatment allocation and implementation of this method will be prepared and finalized prior to randomization of the first participant.

A screen failure is a participant from whom informed consent is obtained and documented in writing, but who is not subsequently randomized to study treatment. Participants who are screen failures are permitted to be rescreened one time (only) according to the PI's discretion. If a participant is rescreened, a new subject ID will be assigned. To link records to the same participant, the participant's previous subject ID will be recorded in the eCRF along with the new subject ID. Participants who complete the rescreening and are randomized in the study will not be considered screen failures.

2.5.2 Blinding

For this double-blind study, the site pharmacists or other designated, licensed study personnel who will prepare and/or administer the study vaccine/placebo will be unblinded to IP assignment. Principal investigators (PIs), all investigational site staff (except those responsible for preparing/administering the IP), representatives of the Sponsor (except unblinded study monitor[s] and unblinded Quality Assurance representatives[s]), representatives of Biomedical Advanced Research and Development Authority (BARDA), contract research organization (CRO) staff (except unblinded statistician and unblinded study monitor[s] and unblinded Quality Assurance representative[s]), and all participants enrolled in this study will be blinded to the IP assignment. To facilitate study oversight while preserving the study blind, a minimum number of CRO and Sponsor personnel will have access to treatment randomization information. The unblinded CRO statistician will have access to the treatment assignment information in the IxRS to support the activities of the DSMB.

Under certain circumstances (e.g., safety reasons, required reporting to regulatory agencies), unblinding of IP for a particular participant is allowed. Otherwise, unblinding of the study will only occur after the clinical database has been locked. Refer to [Protocol EBS.AVA.212, Section 9.6](#) for procedures on how to break the blind for individual participants or procedures in case of accidental participant unblinding.

3 DATA CONSIDERATIONS

3.1 Protocol Deviations

A deviation occurs when site personnel or a participant does not adhere to the protocol's stipulated requirements, whether inadvertently or planned. All identified protocol deviations will be documented (entered in the CRO's Clinical Trial Management System or equivalent), classified, and reviewed on an ongoing basis through out the study according to procedures outlined in the Protocol Deviations Management Plan (PDMP). The final protocol deviation data will be reviewed and locked at the same time of database lock and incorporated into Study Data Tabulation Model (SDTM).

3.2 Analysis Populations

There will be three analysis populations for this study:

The Intent-to-treat (ITT) Population will include all participants who are randomized. Participants will be included in the study group to which they were randomized.

The Safety Population will include all randomized participants who receive at least one vaccination. Safety analyses will be based on the Safety Population according to the vaccine received (BioThrax and combined AV7909 groups).

The Per Protocol (PP) Population will include participants who are randomized and do not have any of the deviations listed below:

- History of previous anthrax disease, anthrax exposure, or anthrax vaccination as per eligibility criteria, as evidenced by a baseline (Day 1 pre-vaccination) TNA NF₅₀ above the limit of detection (LOD).
- Missing or out of window vaccination visit at Study Day 15
- Missing or out of window vaccination visit at Study Day 29 for the BioThrax group
- Administration issue(s) with IP, e.g., incorrect dose of IP at one or more vaccination visits, administration of IP associated with a temperature excursion
- Use of prohibited or restricted medications which may have impacted immune response to vaccination as assessed by the Sponsor (this assessment will be completed prior to database lock)
- Missing immunogenicity data (e.g., sample out-of-window, sample not shipped/received, sample not usable by the immunogenicity lab, sample associated with loss of cold chain) at Day 64

The PP Population will be used for analyses of lot consistency and immunogenicity. Participants will be included in the study group based on the vaccine received.

3.3 Analysis Time Points

Participant visits occur on protocol-specified days with associated visit windows. For purposes of data analysis, if the study day of assessment falls within the visit window, the corresponding analysis visit will be assigned as specified in Table 3 for vaccination, immunogenicity (TNA) testing, clinical laboratory data, vital signs, physical examinations, auto-antibiotic testing, and TSH assessment.

Table 3 Analysis Windows for Vaccination, Immunogenicity (TNA) Testing, Clinical Laboratory Data, Vital Signs, Physical Examinations, Auto-antibiotic Testing, and TSH Assessment

Analysis Visit	Nominal Day	Lower Limit	Upper Limit
Baseline	NA	-28	1, prior to the first vaccination
Day 1	1	1, since the first vaccination	1, since the first vaccination
Day 15	15	14	16
Day 29	29	27	31
Day 64	64	61	67

Out-of-window immunogenicity testing results will be excluded from the analyses for lot consistency and immunogenicity. Data at unscheduled visits might not be presented in the by-visit summary analyses, but will be included in the summary tables by maximum toxicity grade or abnormality and data listings. On vaccination days, vital signs will be taken before vaccination and at 30 minutes (± 5 min) postvaccination, and therefore data will be tabulated for pre- and post-vaccinations, as appropriate.

3.4 Definition of Baseline

For all analyses, the baseline value is defined as the last non-missing value prior to the date and time of the first vaccination.

3.5 Selection of Data in the Event Multiple Records in an Analysis Window

For clinical laboratory data, vital signs, physical examinations, auto-antibiotic testing, and TSH assessment, if multiple valid non-missing observations exist in an analysis window for a specific visit, a single value will be chosen in the by-visit summary analyses based on the following rules:

- For baseline, the last available record prior to the date and time of the first vaccination will be selected.
- For post baseline visits,
 - if the analysis values are numeric and the toxicity grades are available, the record with the highest toxicity grade will be selected;
 - if the analysis values are numeric and the toxicity grades are identical or not available, the average (arithmetic mean) will be used;
 - if the analysis values are categorical, the most conservative value will be selected (e.g., abnormal will be selected over normal).

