For each abnormal laboratory test result, the PI or designee needs to ascertain if this is a clinically significant change from baseline for that individual. This determination, however, does not necessarily need to be made the first time an abnormal value is observed. The PI or designee may repeat the laboratory test and/or request additional tests to verify the results of the original laboratory tests. The PI (or designee) will inform the MM of any unscheduled clinical laboratory testing, including but not limited to confirmatory testing of laboratory samples, with the exception that notification is not required for confirmatory testing for pregnancy, HCV, and HIV. Investigational sites will be alerted by the central laboratory of any Grade 3 or higher laboratory abnormalities. For any Grade 3 or higher laboratory result, the test will be repeated as soon as possible by the central lab to confirm the result. The PI or designee may request the participant return to the clinic for an unscheduled visit for an assessment of clinical status. The decision to redraw laboratory tests will be made by the PI (with notification to the MM) and/or MM and will be based on the type and severity of the laboratory abnormality and the clinical status of the participant. Any Grade 3 or higher neutropenia or lymphopenia must be evaluated with an unscheduled repeat complete blood count (CBC) approximately 72 hours after the initial specimen was drawn, unless a protocol-scheduled CBC has already shown resolution to Grade 1 or lesser toxicity.

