8.3.4. Vital Signs

Vital signs including systolic and diastolic blood pressure (sitting), heart rate, respiration rate, and temperature will be obtained at Screening and each subsequent clinic visit through Day 64/EWV, including unscheduled visits occurring before Day 64. Height and weight will only be recorded at Screening. On vaccination days (Days 1, 15, and 29), vital signs will be assessed prior to vaccination and at 30 ± 5 minutes postvaccination.

The PI or designee will assess vital sign results against toxicity grade criteria (Grade 1=mild through Grade 4=potentially life-threatening) according to the FDA Guidance for Industry: *Toxicity Grading Scale for Healthy Adult and Adolescent Volunteers Enrolled in Preventive Vaccine Clinical Trials* {[CBER, 2007](#)} – refer to [Table 8](#), with grading for oral temperature (fever), heart rate (tachycardia, bradycardia), blood pressure (hypertension, hypotension), and respiratory rate. This grading – assessing severity – will aid in the evaluation of abnormalities and their reporting, if applicable, as AEs.

Any vital sign abnormalities may be followed up with repeat testing. Grade 3 or higher vital signs will be repeated twice to verify that the severity is a Grade 3 or higher. If two of the three assessments are Grade 3 or higher, the vital sign will be reported as a Grade 3 or higher abnormality. All Grade 3 or higher vital sign abnormalities and those vital sign abnormalities determined by the PI or designee to be a clinically significant change from baseline for that participant will be recorded as AEs. As toxicity grading is being used in this study to evaluate and record AE severity (refer to [Section 9.2.1](#)), the vital sign toxicity grade is to be assigned as the AE toxicity grade when reporting on the AE eCRF. Vital sign abnormalities are not to be separately reported as AEs if the abnormality is part of a symptom complex that is already reported as an AE. Vital sign abnormalities may trigger individual participant or study halting rules (refer to [Section 7](#)).

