7.4 Vital Signs

Vital sign data will be assigned a toxicity grade (Grade 1=mild through Grade 4=potentially life-threatening) according to **Protocol EBS.AVA.212, Table 8**. For heartbeat and blood pressure, there are toxicity criteria for both increased and decreased levels; analyses for each direction (i.e., increased, decreased) will be presented separately.

Vital signs data will be summarized as follows:

- Observed values and changes from baseline by study visit and treatment group (AV7909 and BioThrax).
- Shift from baseline according to toxicity grading criteria grade (Grade 0, Grade 1-4) (number and percentages) by study visit and treatment group. Grade 0 includes all values not meeting criteria for toxicity of at least Grade 1.

All vital sign records will be provided in the participant data listings. This listing will include all results that are collected throughout the study for the analyte of interest, with all applicable severity grades displayed. A separate data listing will be provided with Grade 3 or above vital sign observations.

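### After baseline, SAP 3.5 can tabulate a vital sign as Grade 3 on one reading, although Protocol 8.3.4 reports that grade only when two of three readings reach it

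*SAP*

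**What the plan says.** Protocol 8.3.4 sets a verification step: "Grade 3 or higher vital signs will be repeated twice to verify that the severity is a Grade 3 or higher". It then gives the criterion: "If two of the three assessments are Grade 3 or higher, the vital sign will be reported as a Grade 3 or higher abnormality". The same section has Grade 3 or higher abnormalities recorded as adverse events.

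SAP 3.5 names vital signs among the data it governs and applies "if multiple valid non-missing observations exist in an analysis window for a specific visit". One value is then chosen for the by-visit summaries. After baseline, "if the analysis values are numeric and the toxicity grades are available, the record with the highest toxicity grade will be selected". At baseline, "the last available record prior to the date and time of the first vaccination will be selected".

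SAP 7.4 builds a by-visit table from the selected values: "Shift from baseline according to toxicity grading criteria grade", Grades 0 to 4, by treatment group. It also provides a listing of Grade 3 or higher observations.

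The two-of-three criterion does not appear in SAP 2.2.3.4, 3.5, 3.8 or 7.4. SAP 2.2.3.1 points to Protocol 8.3.4, but only for the reporting of adverse events.

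**The concern.** The protocol's repeats exist to separate a real Grade 3 finding from a single high reading. The reading that prompts the repeats is Grade 3 or higher by definition. A rule that picks the highest grade in the window therefore returns Grade 3 or higher whatever the repeats show, and verification has no effect on the by-visit table.

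At baseline the last record is used, so a high first reading gives way to whatever the final repeat shows. The same three readings can be below Grade 3 at baseline and Grade 3 afterwards.

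At stake is the meaning of the vital-sign shift tables. They could show Grade 3 values that the protocol's own criterion rejects, some apparent worsening after vaccination that comes from record selection, and Grade 3 entries with no matching adverse event, because event recording does follow 8.3.4.

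**Working it through.** The documents state no rate on this point, so there is no plan figure to reproduce. The check compares the three rules on the same readings and then sizes the gap.

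**Step 1: every outcome of one Grade 3+ reading and two repeats.**

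| Readings in order | Protocol 8.3.4 | SAP 3.5, post-baseline | SAP 3.5, baseline |
|---|---|---|---|
| 3+, below, below | below | **3+** | below |
| 3+, below, 3+ | 3+ | 3+ | 3+ |
| 3+, 3+, below | 3+ | 3+ | **below** |
| 3+, 3+, 3+ | 3+ | 3+ | 3+ |

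Bold marks disagreement with the protocol. Example: in Protocol Table 8, systolic pressure above 155 mmHg is Grade 3 and 141–150 is Grade 1. Readings of 158, 146 and 142 have one of three at Grade 3, so the protocol does not report Grade 3. SAP 3.5 gives Grade 3 after baseline and Grade 1 (the last reading, 142) at baseline.

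**Step 2: how often the post-baseline rule keeps an unconfirmed value.** Let p be the chance that each repeat is again Grade 3+, with independent repeats. This is an assumption; the documents give no value.

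- Confirmed share of triggered visits = 1 − (1 − p)²
- Unconfirmed share = (1 − p)²
- Share tabulated as Grade 3+ under SAP 3.5 = 100% at every p

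| p | Confirmed | Unconfirmed but tabulated |
|---|---|---|
| 0.1 | 19% | 81% |
| 0.3 | 51% | 49% |
| 0.5 | 75% | 25% |
| 0.7 | 91% | 9% |
| 0.9 | 99% | 1% |

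**Step 3: direction and size in the shift table.** Let q be the chance that a time point has a first reading of Grade 3+, the same at baseline and later, with no true change and independent time points (all assumed). Write c = 1 − (1 − p)².

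- SAP rules: up-shift = (1 − qp) × q; down-shift = qp × (1 − q)
- Protocol criterion at both times: up-shift = down-shift = (1 − qc) × qc

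With q = 0.02 and p = 0.5, c = 0.75:

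- SAP up: (1 − 0.010) × 0.020 = 1.98%
- SAP down: 0.010 × (1 − 0.020) = 0.98%
- Protocol, each way: (1 − 0.015) × 0.015 = 1.48%

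Nothing has changed in these participants, so up and down should balance. Under the SAP rules up exceeds down by 1.00 percentage point, and the up-shift rate is 1.98/1.48 = 1.34 times the protocol-criterion rate.

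For q from 0.01 to 0.05 that ratio is about 2.0 at p = 0.3, 1.3 at p = 0.5 and 1.1 at p = 0.7. In absolute terms the excess in up-shifts runs from about 0.1 point (q = 0.01, p = 0.7: 0.993% − 0.902%) to about 2.4 points (q = 0.05, p = 0.3: 4.925% − 2.485%).

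**Step 4: effect of correcting only the post-baseline rule.** At q = 0.02 and p = 0.5, up = (1 − 0.010) × 0.015 = 1.485% and down = 0.010 × (1 − 0.015) = 0.985%. The excess of up over down falls from 1.00 to 0.50 point. The rest comes from the last-record baseline and disappears only if the baseline grade is also confirmed (1.48% each way).

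**The case against.** The strongest reply has four parts.

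- **The effect depends on data capture.** SAP 3.5 acts only when several valid records share a window. The documents do not say how repeats enter the eCRF, and valid is not defined. SAP 3.8 has the investigator or designee assess vital-sign severity, so a recorded grade may already reflect 8.3.4. SAP 3.3 may leave unscheduled-visit data out of by-visit tables. This stands as a condition on the finding, but the SAP says nothing that removes the conflict.
- **Protocol 10.6.5 itself asks for vital-sign abnormalities by highest toxicity grade.** True, but that does not cancel 8.3.4, which defines when a vital sign is reported as Grade 3 or higher in the first place.
- **The baseline rule is the protocol's.** Protocol 10.6.5 and SAP 3.4 both take the last value before first vaccination. This stands. A reader might infer that the baseline value should be replaced by a median or a confirmed reading; that would put the SAP in breach of the protocol's definition.
- **The impact is small.** The rule is the same in both arms, errs toward over-reporting, and feeds descriptive tables with no hypothesis test. This stands, and it sets the severity.

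A reader might also extend the point to laboratory data, where for a Grade 3 or higher result "the test will be repeated as soon as possible by the central lab to confirm the result", and so to the secondary endpoint on laboratory abnormalities. The documents do not support this. Protocol 8.3.2 has no majority rule: a Grade 3 or higher value on either the retested sample or the repeat counts as an adverse event, and nothing says a superseded run is kept as a second valid record.

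**Conclusion.** The point holds for post-baseline vital signs and is minor. The SAP's selection rule contradicts the protocol's Grade 3 criterion, and no SAP section reconciles them. Where repeats are stored as separate valid records in the window, every triggering reading is tabulated as Grade 3 or higher. The part that the protocol would not report is 49%, 25% or 9% of triggered visits at p = 0.3, 0.5 or 0.7. These shares rest on an assumed p and on independent repeats. The shift rates rest further on an assumed trigger rate of 1% to 5%, no true change and independent time points. They show direction and rough scale and do not predict the trial's counts.

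Together with the last-record baseline, the mismatch pushes shifts upward in both arms. A reader might infer a bias against AV7909 relative to BioThrax; the documents give no ground for that, since both groups follow the same rule. Vital-sign adverse events follow 8.3.4 and are less affected. Vital-sign grade shifts are not a listed primary or secondary endpoint, and immunogenicity results, type I error and power are untouched.

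**What to change.** Add one sentence to SAP 3.5, with a cross-reference in 7.4: for post-baseline vital signs, the two-of-three rule of Protocol 8.3.4 is applied before the highest-grade record is selected, so an unconfirmed Grade 3 or higher reading cannot be selected at that grade. It stays in the listings with a flag. In the 158, 146, 142 example the two remaining readings are both Grade 1, and the existing SAP 3.5 rule for identical grades gives their mean, (146 + 142)/2 = 144.

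Leave the baseline value as the last measurement before vaccination. If the baseline grade is meant to be comparable, apply the same confirmation rule to the grade only and say so.

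The cost is one sentence and a few lines of derivation code, plus a check of how the eCRF stores repeat readings. The downside is that unconfirmed single Grade 3 or higher readings then appear only in listings. No change to the laboratory rules is needed on this account.
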